5.1.3.2 Post therapies date imputation

Not applicable

5.1.4 Medical History date of diagnosis imputation

Completely missing dates will not be imputed. Partial dates of diagnosis will be compared to the treatment start date.

- If DIAG year < study treatment start date year and DIAG month is missing, the imputed DIAG date is set to the mid-year point (01JULYYYY)
- Else if DIAG month is not missing, the imputed DIAG date is set to the mid-month point (15MONYYYY)

If DIAG year = study treatment start date year and (DIAG month is missing OR DIAG month is equal to study treatment start month), the imputed DIAG date is set to one day before study treatment start date

5.2 AEs coding/grading

The verbatim term recorded on CRF will be identified as adverse event and will be coded by primary system organ class and preferred term using Medical Dictionary for Regulatory Activities (MedDRA) version 18.1 and above.

5.3 Laboratory parameters derivations

Refer to main section of SAP.

5.4 Statistical models

5.4.1 Primary analysis

The null hypothesis to be rejected is that the odds of response at Week 8 are equal in both treatment groups. The corresponding alternative hypothesis is that the odds of response at Week 8 are higher under secukinumab compared to placebo.

The primary analyses will be conducted via logistic regression model with treatment, country and the stratification factor of prior exposure to TNF inhibitors (naïve/ inadequate responders to TNF α inhibitors) as factors. The Odds ratio, 95% confidence interval (CI) and p-value will be presented comparing secukinumab 150 mg treatment group to placebo group at Week 8.

SAS Code for logistic model

```
Proc logistic data=aaa;
Class TRT STRATA / param=glm;
Model AVAL = TRT COUNTRY STRATA;
Lsmeans TRT / diff cl exp;
Ods output diffs=lsm_diff;
Run;
```

In cases where separation is a concern for the primary endpoint at Week 8, e.g. 0% or 100% response in one treatment (sub)group, an exact logistic regression model will be applied to all visits. To ensure convergence, this model will not include any continuous covariates.

```
Proc logistic data=aaa exactonly;
Class TRT STRATA / param=glm;
Model AVAL = TRT COUNTRY STRATA;
Exact TRT / estimate=both;
Ods output exactoddsratio=exactoddsratio;
Run;
```

In addition to that the above analysis will also be performed a sensitivity analysis for raw spinal pain NRS score.

Mixed Model Repeated Measures (MMRM)

The following MMRM (or repeated measures ANOVA) model will be used for analysis of raw (total & nocturnal) and average spinal pain NRS score:

```
proc mixed data=.... order=internal;
where vis_1n in (2, 3, 4, 5, 6, 7);
class trt country strata;
model val_1n = trt bsval_1n country strata/ddfm=kr;
repeated vis_1n / subject=sid1a type=un;
lsmeans trt/ cl diff;
```

run;

If type=Unstructured (un) fails, we will use Compound Symmetry (cs)

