## 5.3 Treatment assignment and randomization

At Baseline, all eligible patients will be randomized to one of the treatment groups (Group A and Group B) via an Interactive Response Technology (IRT) system or similar system. The investigator or his/her delegate will contact the IRT after confirming that the patient fulfills all the inclusion/exclusion criteria. The IRT will assign a randomization number to the patient, which will be used to link the patient to a treatment group and will specify a unique medication number for the first package of study drug to be dispensed to the patient. The randomization number will not be communicated to the caller.

Randomization at Baseline will be stratified based on prior TNF $\alpha$  inhibitor exposure (i.e. according to whether patients are TNF $\alpha$  inhibitor naïve or TNF $\alpha$ -IR). It is assumed that approximately one third of the randomized patients will be TNF $\alpha$ -IR.

At Week 8, patients randomized to Group A (secukinumab 150 mg) at Baseline will be assessed for the achievement of spinal pain NRS score and will be classified as responders (spinal pain NRS score  $< 4$ ) or non-responders (spinal pain NRS score  $\geq 4$ ) and re-randomized or re-assigned via IRT to one of the treatment arms (Arm A1, Arm A2, Arm A3) as outlined in Section 5.2. At Week 8, patients randomized to Group B (placebo) at Baseline will be re-randomized via IRT to one of the 2 treatment arms (Arm B1 or Arm B2) as outlined in Section 5.2.

The IRT will be used to link the patient to a treatment group/arm and will specify unique medication numbers for the study drug to be dispensed to the patient. The randomization

numbers will not be communicated to the caller and will be generated using the following procedure to ensure that treatment assignment is unbiased and concealed from patients and investigator staff. A patient randomization list will be generated in collaboration with the IRT provider using a validated system that automates the random assignment of patient numbers to randomization numbers. These randomization numbers are linked to the different treatment groups/arms, which are in turn linked to medication numbers. A separate medication list will be produced in collaboration with Novartis Drug Supply Management using a validated system that automates the random assignment of medication numbers to packs containing the investigational drugs.

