2.5.2 Statistical hypothesis, model, and method of analysis

The null hypothesis to be rejected is that the odds of response at Week 8 are equal in both treatment groups. The corresponding alternative hypothesis is that the odds of response at Week 8 are higher under secukinumab compared to placebo.

Let p_j denote the proportion of responders at Week 8 for treatment group j , $j=0, 1$, where

- 0 corresponds to placebo
- 1 corresponds to secukinumab

In statistical terms, the following hypothesis will be tested:

$H_0: (p_1 / (1 - p_1)) / (p_0 / (1 - p_0)) = 1$ versus $H_A: (p_1 / (1 - p_1)) / (p_0 / (1 - p_0)) \neq 1$

In other words,

H_A : The odds ratio of achieving a response at Week 8 for secukinumab vs. placebo is different from 1.

The primary analyses will be conducted via logistic regression model with treatment, country and the stratification factor of prior exposure to TNF inhibitors (naïve/ inadequate responders to TNF α inhibitors) as factor. The Odds ratio, 95% confidence interval (CI) and p-value will be presented comparing secukinumab 150 mg treatment group to placebo group at Week 8.

The null hypothesis of equal odds will be rejected if the 2-sided p-value from the logistic regression model for the factor “treatment” is < 0.05 ; however, superiority of secukinumab will be claimed only if the direction is correct, i.e. if the odds of response are larger under secukinumab.

Summary statistics will also be reported for each treatment group and by visit. Graphical representation will also be performed.

Grouping of countries: Due to the small number of subjects in some of the countries, the below mentioned countries will be grouped together to perform inferential analysis. The basis of grouping is a similar medical practice and geographical proximity in these countries:

- 1) Ireland & Great Britain
- 2) Italy, Spain & Croatia
- 3) Switzerland & Belgium
- 4) Finland & Sweden
- 5) Lithuania, Latvia & Estonia

If the grouping of countries does not allow proper analysis and if there are any challenges in model convergence, covariate “country” will be excluded from model.

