2.5.4 Sensitivity analyses

The average spinal pain and raw (total and nocturnal spinal pain separately) NRS scores will be analyzed using a repeated measures analysis of variance (ANOVA) model. The model will include the same factors as the logistic model of primary analysis plus the respective baseline score as a covariate. Analysis visit will be used as repeat factor.

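### The SAP 5.4.1 logistic code leaves country out of CLASS, and the repeated-measures sensitivity model has no visit or treatment-by-visit effect, so it gives no Week 8 contrast

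*SAP*

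**What the plan says.** **Primary model.** SAP 2.5.2 calls for a "logistic regression model with treatment, country and the stratification factor of prior exposure to TNF inhibitors", names country as a factor and pools small countries into five named groups. It drops country only as a fallback: "If the grouping of countries does not allow proper analysis", or if the model has convergence problems. SAP 5.4.1 repeats the description and then prints two PROC LOGISTIC steps. Both contain "Class TRT STRATA / param=glm" and "Model AVAL = TRT COUNTRY STRATA". The second is the exact model, introduced with the statement "To ensure convergence, this model will not include any continuous covariates".

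**Sensitivity model.** SAP 2.5.4 has one sensitivity analysis, a repeated-measures ANOVA of the average, total and nocturnal pain scores: "The model will include the same factors as the logistic model of primary analysis plus the respective baseline score as a covariate". Visit appears once: "Analysis visit will be used as repeat factor". SAP 2.13 describes the same model and asks for one least squares mean difference between the two groups. The PROC MIXED code in SAP 5.4.1 puts treatment, country and stratum in CLASS. Its fixed effects are treatment, baseline score, country and stratum. The visit variable `vis_1n` appears in WHERE (codes 2 to 7) and REPEATED only, and the only estimate requested is the LS-mean difference for treatment. The covariance is unstructured, with compound symmetry as fallback. Protocol 9.4.4 adds no visit term.

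**The concern.** Two things on the page do not do what the plan needs.

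First, a variable in MODEL but not in CLASS is treated as continuous. If COUNTRY is stored as text, the step stops. If it is numeric, one slope is fitted across arbitrary codes. The SAP does not state the storage type. The exact step would also contain what its own introduction excludes.

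Second, SAP 1.1 ties the primary analysis to Week 8, and the repeated-measures model is the only listed check on it. A model with one treatment coefficient and no visit terms cannot return a Week 8 difference. If pain relief builds up over the first weeks, which this trial sets out to study, the pooled difference understates the Week 8 difference. It could then be misread as evidence for or against the robustness of the primary result. The same model is run for three scores.

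**Working it through.** **1. Country: text against code.** The text (SAP 2.5.2 and 5.4.1) makes country a factor. Both logistic steps leave it out of CLASS, while the PROC MIXED step includes it. The intent is therefore clear and the logistic code is the slip.

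**2. Visit: text against code.** Here the two agree, and both lack the term. SAP 2.5.4 takes over the logistic factors (treatment, country, stratum) plus baseline, and the MODEL statement matches. `vis_1n` is in REPEATED but not in CLASS, so the step should not run as printed. The smallest repair, adding it to CLASS only, still leaves one treatment coefficient.

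**3. What the repaired model estimates.** With effects δ(t) at the visits, the coefficient is Σ w(t)·δ(t), with weights summing to 1. Under compound symmetry and complete data each of the five visits has weight 1/5. Under an unstructured covariance, the fitted matrix also absorbs the omitted time trend, so the weights depend on the SDs, the correlations and the trend.

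**4. Size.** The documents give no onset curve, SD or correlation, so all are assumed. Onset as a fraction of the Week 8 effect is f(t) = (1 − 2^(−t/h)) / (1 − 2^(−8/h)) for half-life h weeks, or t/8 if linear.

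| Onset | f at Weeks 1, 2, 3, 4, 8 | CS: sum/5 | CS, baseline rows kept: sum/6 | UN range |
|---|---|---|---|---|
| Immediate | 1, 1, 1, 1, 1 | 100% | 83% | 100% |
| h = 1 | .502, .753, .878, .941, 1 | 81% | 68% | 60-81% |
| h = 2 | .312, .533, .690, .800, 1 | 67% | 56% | 42-67% |
| h = 4 | .212, .391, .541, .667, 1 | 56% | 47% | 31-56% |
| Linear | .125, .25, .375, .5, 1 | 45% | 38% | 19-45% |

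For linear onset: (0.125 + 0.25 + 0.375 + 0.5 + 1)/5 = 2.25/5 = 0.45, and 2.25/6 = 0.375.

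Each UN range (five post-baseline visits) covers 3 SD patterns × 6 correlation patterns × 3 placebo changes × 3 Week 8 effects = 162 settings. For linear onset, flat SDs give 38-45%, rising SDs 28-35% and steeply rising SDs 19-27%. A simpler calculation without the baseline covariate, on a different grid, gave 45-56% for linear onset with flat SDs, so the UN figures are illustrative.

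A separate simulation (SD 2, AR(1) correlation 0.6, true Week 8 difference −1.5 points) gave these pooled values:

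| Onset | UN | CS |
|---|---|---|
| Linear | −0.62 | −0.68 |
| Plateau by Week 4 | −0.88 | −1.06 |
| Late | −0.45 | −0.47 |
| Constant effect | −1.49 | −1.48 |

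With visit and treatment-by-visit added, the Week 8 contrast was −1.48 to −1.52. In a further check with 264 and 88 patients (13 settings, 150 trials each) it was −1.46 to −1.55.

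**5. Visit codes.** Treatment Period 1 has five post-baseline visits (Protocol Table 6-1), but WHERE keeps six codes. Under the protocol's visit numbers, 7 is Week 8 and 2 is Baseline, which is already the covariate. `vis_1n` is not defined, and the SAP does not say whether the data set holds baseline rows.

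**6. Country: size.** The plan's rates give OR = (0.436/0.564)/(0.235/0.765) = 2.52. Simulation: 352 patients at 3:1, one third TNFα-IR, 8 or 12 countries of unequal size, 2000 trials per setting.

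| Between-country SD (logit) | Power, factor | Power, slope | p < 0.05 call differs |
|---|---|---|---|
| 0 | 92-94% | 92-94% | 1.2% |
| 0.5 | 92% | 91-92% | 3.1-3.9% |
| 1.0 | 90-91% | 86% | 7.2-7.3% |

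Type I error is 4.4-5.7% with the factor and 4.4-5.9% with the slope. This is expected, since "Randomization at Baseline will be stratified based on prior" TNFα inhibitor exposure alone and country plays no part. The 1.2% at SD 0 is the reference level of disagreement. Trials with 0% or 100% response in a country were set aside because the SAP fallbacks could apply: 0.1-15.9% of trials at OR 2.52 and 0.8-43.8% at OR 1, rising with the country SD.

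**7. Sample size.** The plan's 332 reproduces with the continuity-corrected two-proportion formula (83 + 249; uncorrected 77 + 231 = 308). Nothing here changes it.

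**The case against.** The strongest reply has five parts.

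- **Country is trivial.** The text fixes the factor, a text-valued COUNTRY would stop the run and be noticed, and SAP 2.5.2 even allows country to be dropped. This stands, and alone the slip would be minor. The simulation figures also exclude the trials in which the fallbacks might apply, so they do not describe the full planned procedure.
- **No Week 8 mean contrast is promised.** A difference averaged over Treatment Period 1 is a legitimate quantity. It is true that the SAP makes no express promise. But the model is the only sensitivity analysis of a Week 8 endpoint, and an average over visits does not test that.
- **The wording can be read as visit-wise.** SAP 2.13 introduces its list as covering every applicable visit, and SAP 5.4.1 labels the model MMRM. That may be the intent, but neither adds a visit term or changes the single LS-mean difference requested.
- **The percentages rest on assumed inputs and a repaired model.** This is correct. They show direction and plausible size only. The lowest values need SDs that rise steeply over visits.
- **Little is at stake.** The model carries no alpha, and Week 8 summaries by group are reported anyway. A continuous Week 8 contrast would still not test the non-responder imputation. All true, but descriptive summaries do not replace a correctly specified analysis.

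The unclear sentence in SAP 5.4.1 about repeating the above analysis for raw scores most naturally refers to the repeated-measures model that follows it. It needs only a clarification. If it meant the logistic step, it would cover the total and nocturnal scores, not the average that defines response.

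**Conclusion.** The point holds and should be fixed. The missing visit and treatment-by-visit effects are the substantive fault, because text and code share it and neither repairs the other. Once made to run, the model gives one pooled difference that equals the Week 8 effect only under a constant effect. Under the gradual-onset curves in the table it falls to 45-81% of the Week 8 effect with compound symmetry. With an unstructured covariance it can be lower still, depending on the assumed SDs and correlations.

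The country slip is a conflict between code and text. It has no material effect on type I error, and it costs appreciable power only if countries differ strongly and COUNTRY is numeric. The extra disagreement in the p < 0.05 call is about 2-3 points at a country SD of 0.5 and 6 points at 1.0. The primary model as worded, the sample size and the alpha are unaffected.

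**What to change.** 1. Add the grouped country variable of SAP 2.5.2 to CLASS in both PROC LOGISTIC steps. Apply the same correction to the BASDAI analysis, which SAP 2.7.2 defines by analogy. Naming the event level is optional but makes the direction of the odds ratio explicit.
2. Define `vis_1n`, and restrict the outcome rows to Weeks 1, 2, 3, 4 and 8, with baseline as covariate only.
3. Add visit to CLASS, and visit and treatment-by-visit to MODEL. State both terms in SAP 2.5.4 and 2.13.
4. Report the Week 8 treatment contrast from the treatment-by-visit LS-means. The pooled difference can be kept as an additional, labelled summary.
5. Say which analysis the raw-score sentence in SAP 5.4.1 refers to.

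The cost is a few lines of code and wording. No new data are needed, and the sample size and testing order do not change.

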★ Patients will be stratified at baseline based on whether they are naïve to TNF α inhibitors or had an inadequate response (including intolerance) to TNF α inhibitors.

R+ = responder, i.e. patient with spinal pain NRS score < 4

R- = non-responder, i.e. patient with spinal pain NRS score \geq 4

axSpA=axial spondyloarthritis, BSL=baseline, PE=primary endpoint, SE=secondary endpoint, TNF α =tumor necrosis factor alpha, TNF α -IR=tumor necrosis factor α inadequate responder, W=week

Primary analysis time point

The primary analysis will be performed based on Week 8 assessment data. Average spinal pain NRS score will be considered as primary endpoint and will be analyzed for all applicable variables.

Interim analyses

No interim analysis is planned for this study.

The statistical analysis will be performed after all the patients have completed the study. Once all the data are complete and clean, the database will be locked and analyzed.

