2.14 Interim analysis

No interim analysis is planned for this study.

3 Sample size calculation

To assess the assumed effect size at Week 8, a 43.6% response rate (spinal pain NRS < 4) is assumed for the secukinumab 150 mg group. This number is derived as an average of the response rates observed in the CAIN457F2320 and CAIN457F2310 studies ([Baeten et al 2015](#)). For the placebo group, a response rate at Week 8 of 23.5% (NRS < 4) was selected as assessed in the CAIN457F2320 study. This intermediate scenario takes into consideration a certain likelihood of a relatively high placebo response also in line with data from the TNF α reference studies and the CAIN457F2305 study in addition to the slightly milder course of the disease in the studied population ([Baeten et al 2015](#)).

Assuming conservatively a response rate of 23.5% in the placebo group and a response rate of 43.6% under secukinumab 150 mg, 332 patients in total (i.e. 249 patients in secukinumab 150 mg group and 83 patients in placebo group) would be needed under 3:1 (secukinumab: placebo) allocation to achieve 90% power on a (2-sided) 5% significance level. To compensate for drop-out patients or those with protocol deviations, a total of 352 patients (264 in secukinumab 150 mg group and 88 in the placebo group) should be recruited.

4 Change to protocol specified analyses

None.

5 Appendix

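### The SAP gives two overlapping, unordered fallbacks for the primary logistic model, and its example of separation is wider than separation in that model.

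*SAP*

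**What the plan says.** The primary analysis is a logistic regression on treatment, country and TNF stratum, judged by the two-sided p-value for treatment (SAP 2.5.2, repeated in 5.4.1). Two fallbacks follow in different places.

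- **SAP 2.5.2** merges small countries into five listed groups. It then sets two joint conditions: the grouping does not allow proper analysis, and, in the SAP's words, "if there are any challenges in model convergence, covariate"; the sentence goes on to remove country from the model.
- **SAP 5.4.1** opens its rule by naming separation at Week 8 as the concern, then gives an example and an action: "e.g. 0% or 100% response in one treatment (sub)group, an exact logistic regression model will be applied to all visits". Its exact code keeps country in the model statement.

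Neither section refers to the other, sets an order, or says who decides and when. The term (sub)group is not defined, and the SAP does not say which exact p-value is compared with 0.05. On timing, SAP 1.1 says "Once all the data are complete and clean, the database will be locked and analyzed". Protocol 5.4 keeps analysts blind until lock, and Protocol 8.3 releases the treatment codes after it.

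**The concern.** A country factor with few patients per level is the likeliest source of both non-convergence and separation, and separation is itself a cause of non-convergence. One dataset can therefore meet both rules. One leads to a Wald test without country, the other to an exact test with country. With the stated Wald test, that makes three candidate p-values for the one confirmatory comparison that also gates BASDAI.

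Two features make this more than missing detail. Response by treatment group, and convergence of a model that contains treatment, can only be examined with the codes in hand. And if the 5.4.1 example is applied to arm-by-country cells, it would bring in the exact test when the planned model has no difficulty.

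**Working it through.** **1. Inputs.** From SAP Section 3: "a 43.6% response rate (spinal pain NRS < 4) is assumed for the secukinumab 150 mg group"; "Assuming conservatively a response rate of 23.5% in the placebo group"; "249 patients in secukinumab 150 mg group and 83 patients in placebo group"; "a total of 352 patients (264 in secukinumab 150 mg group and 88 in the placebo group) should be recruited"; and the aim "to achieve 90% power on a (2-sided) 5% significance level". From Protocol 5.3: about one third of patients are TNF inadequate responders. The number and size of countries are not given, so everything below that depends on them is an assumption.

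**2. The plan's own figure.** Pooled rate = (0.235 + 3 × 0.436)/4 = 0.38575; difference = 0.201. Placebo n without continuity correction = [1.960 × √(4/3 × 0.38575 × 0.61425) + 1.2816 × √(0.235 × 0.765 + 0.436 × 0.564/3)]² / 0.201² = (1.1016 + 0.6557)² / 0.0404 = 76.4. With continuity correction: (76.4/4) × [1 + √(1 + 8/(3 × 76.4 × 0.201))]² = 82.9, so 83 placebo and 332 in total. The stated size is reproduced.

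**3. What separates TRT + COUNTRY + STRATA.** A coefficient can diverge only along a direction that leaves every cell with mixed responses unchanged. Suppose one arm-by-country cell is at 0% and the rest are mixed. The other countries then fix the treatment direction at zero, and the other arm of the same country fixes that country's direction at zero, so nothing can diverge. A whole country at 0% or 100% makes that country's coefficient diverge. A whole arm at 0% or 100% makes the treatment coefficient diverge, but for placebo the chance of 0% is 0.765^88 ≈ 6 × 10⁻¹¹.

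**4. How often the example would occur if read as arm-by-country cells.** With C equal country groups, an empty placebo cell dominates: P ≈ 1 − (1 − 0.765^(88/C))^C.

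| C | 5 | 8 | 10 | 12 | 15 |
|---|---|---|---|---|---|
| P | 4% | 35% | 63% | 84% | 97% |

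Simulations used N = 352, unequal groups, country SD 0.5 and TNF effect −0.4 on the logit scale. They give 79% for 8 groups and 99% for 12. Other assumed structures give about 22% to over 99%.

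**5. How often the model is really in trouble.** In the same simulations a whole country at 0% or 100% occurs in 0.6% (8 groups) and 5.3% (12 groups) of trials; other structures give 0-20%. Whenever a cell was at 0% or 100% but no whole country was, the planned model converged (1,561 of 1,561 and 1,870 of 1,870 trials at the design rates). Whenever a whole country was, it failed the convergence check. That is where both fallbacks apply. Yet in a worked case the treatment estimate was 1.441 (SE 0.323) whether the separated country was kept or deleted, so no switch was needed for treatment.

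**6. What the choice does to the result** (% of trials with p < 0.05; 2,000, 1,500 and 4,000 trials per row for the design, weaker-effect and null settings):

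| Rates, groups | Wald with country | Wald without | Exact | Best of three | Tests disagree |
|---|---|---|---|---|---|
| 23.5 v 43.6, 8 | 92.5 | 92.0 | 91.5 | 93.9 | 3.6 |
| 23.5 v 43.6, 12 | 92.2 | 91.5 | 90.6 | 93.4 | 4.2 |
| 23.5 v 35, 8 | 50.5 | 48.1 | 47.3 | 53.9 | 10.8 |
| 23.5 v 35, 12 | 53.5 | 52.3 | 51.0 | 57.3 | 9.9 |
| 30 v 30, 8 | 5.4 | 4.9 | 4.3 | 6.3 | 2.7 |
| 30 v 30, 12 | 5.5 | 5.3 | 4.5 | 6.8 | 3.2 |

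Over the wider set of structures, the two fallbacks disagree with each other in about 3-6% of trials at the design rates and about 7-9% at 38% v 26%. Best-of-three rejection under the null is about 5.4-6.8%.

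**The case against.** The strongest reply is that this is a drafting gap with little at stake. The 5.4.1 sentence does name separation as its trigger, and the 0% or 100% clause is only an example, valid for a whole arm. The 2.5.2 rule needs two conditions together and comes after prespecified grouping. At the design rates every fixed test has power of about 87-94% across the structures tried. The best-of-three figure assumes a free choice in every trial. If a choice arose only where a whole country is separated (1.7% and 13.8% of the null trials), the excess would be roughly 0.9 × 0.017 ≈ 0.02 and 1.3 × 0.138 ≈ 0.18 percentage points, taking the two as independent. The early visits affected by the all-visits clause are exploratory.

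All of that stands as a limit on size. It does not supply an order between the rules or define (sub)group. The small excess also requires both rules to be held to true separation, which the SAP wording does not ensure.

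A reader might infer that the 5.4.1 trigger is something other than separation, or that the exact test would almost always replace the stated one. The documents do not support either: the sentence requires a separation concern first, and treatment-by-country is only one reading of (sub)group.

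**Conclusion.** The point holds as a conflict between two sections over which p-value is confirmatory. The fallbacks overlap and are unordered; they are not irreconcilable, since one sentence could rank them. The separation example is faulty only for arm-by-subgroup cells, where acting on it would replace the planned test with a more conservative one (null rejection 4.3-4.5% against 5.4-5.5%) without need.

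The consequence is small at the design rates and matters mainly for a borderline result. The existence of the conflict rests on the text alone. All frequencies rest on assumed country numbers, sizes and spread, and should be read as ranges; with five equal groups the cell event falls to 4%.

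A reader might also infer that the model would be picked on unblinded results. The documents do not say that. They say neither who decides nor when, and a whole-country check could be made on blinded pooled data. What follows from the text is narrower: triggers that need treatment group, or a fit containing treatment, cannot be checked before the codes are released.

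**What to change.** Use one ordered rule, worded identically in SAP 2.5.2 and 5.4.1.

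1. Finalise the country grouping on blinded pooled data before lock, with the merge target named in advance for every country, including those outside the five listed groups.
2. Keep TRT + COUNTRY + STRATA as primary unless the treatment estimate itself does not exist, that is, the software reports complete or quasi-complete separation affecting TRT. State that a warning about a country coefficient alone does not trigger a switch. Delete the arm-by-subgroup example and the sentence that drops country.
3. Name one substitute model and one p-value for that case, at the affected visit only: either exact logistic regression with the same factors and a stated exact p-value, or Firth regression with the penalised likelihood-ratio p-value. Any other version is supportive.
4. Apply the same rule to BASDAI.

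The cost is SAP wording and a small code edit, with no new data. In the same edit, add COUNTRY to the CLASS statement of both logistic code blocks; it is missing there, although the text treats country as a factor.
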